8.2. Outcome analyses

For samples where LcS is not detected, counts will be set to the limit of detection to allow for statistical analysis¹. Descriptive plots will be provided for the distribution of LcS at each time point (i.e. boxplots) as well as line graphs for each subject. LcS number over time will be analyzed with a repeated measures model with an unstructured covariance structure where the LcS number at each time point will be included in the response vector. The model derived absolute change in LcS from baseline (day 14) to each of days 21, day 28, and 42 will be estimated along with the corresponding 95% confidence interval. In the event model assumptions are violated (i.e. constant variance and/or normality of residuals), a log transformation followed by a rank transformation will be considered. Note, if a rank transformation is used, contrast statements will be used to test the change from baseline but an estimate will not be calculated.

It is possible that the baseline LcS number for all subjects will be non-detectable which would likely result in the model assumption failure. If there are no detectable LcS levels at baseline and the repeated measure model assumptions are violated after exploring possible data transformations, then a model will be fit that only considers the post-consumption time points where the subject is on active product (day 21 and day 28). The estimated mean and 95% CI at day 21 and day 28 would then reflect an estimated increase from baseline. The proportion of subjects that return to baseline (day 14) by day 42 will be estimated along with a 95% CI. Additionally, in the subset of subjects that have elevated LcS while on study product measured at day 21 or day 28, as compared to baseline (day 14), the proportion of subjects that return to baseline by day 42 will be estimated along with a 95% CI.

Product emergent-AEs and SAE will be described. The proportion of subjects with at least 1 possibly, probably, or definitely related AE will be estimated along with the corresponding 95% CI.

9. Handling of missing data

For outcomes measured at multiple time points post baseline, statistical models that account for unbalanced data will be used. Specifically, missing data will be handled by maximum likelihood estimated of mixed models which assumes data is missing at random.

10. Deviations from statistical plan and other issues

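### SAP 8.2 checks for equal variance, which its unstructured model does not assume, and can end in a rank test with no estimate when only some baselines are detectable

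*SAP*

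**What the plan says.** The main analysis is set out in SAP 8.2: "LcS number over time will be analyzed with a repeated measures model with an unstructured covariance structure". Visit is the only effect named. Non-detects are handled in the same section: "For samples where LcS is not detected, counts will be set to the limit of detection to allow for statistical analysis". The model starts on the untransformed count.

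The rule for leaving that scale begins "In the event model assumptions are violated (i.e. constant variance and/or normality of residuals" and continues that "a log transformation followed by a rank transformation will be considered". If ranks are used, "contrast statements will be used to test the change from baseline but an estimate will not be calculated". The SAP names no test or cut-off for judging a violation.

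One special case is foreseen: "It is possible that the baseline LcS number for all subjects will be non-detectable which would likely result in the model assumption failure". The remedy is a model of Days 21 and 28 only, whose means and 95% CIs stand for the increase from baseline. It is conditional: "If there are no detectable LcS levels at baseline and the repeated measure model assumptions are violated after exploring possible data transformations". The scale of this fallback is not stated.

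The protocol differs on scale. The synopsis log-transforms the counts from the outset. Protocol 12.3.2 treats a log or rank transformation as something to consider after a violation. Both contain the same trigger on variance and normality.

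**The concern.** An unstructured covariance estimates a separate variance at each visit. Unequal variances across visits are therefore part of the model, not a breach of it. With visit as the only named effect, the natural reading of the variance check is a comparison across visits, so the SAP tests for something its model does not need.

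The data are likely to fail that check. At Days 14 and 42 most values may be the LOD itself; at Days 21 and 28 counts should be near 10^7 per gram (protocol 4.4) and vary widely between people. Pooled residuals would then mix a spike at one value with a broad spread, so the normality check is likely to fail too.

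At stake is the estimate and interval for the primary endpoint (SAP 5.1), in a study whose purpose is to describe how much of the strain survives. A rank test would say that counts rose but not by how much.

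**Working it through.** **What the model needs.** With complete data, the unstructured-model contrast for Day 28 against Day 14 is the mean of the within-person differences d = Y28 - Y14, with interval mean(d) ± t(0.975, 24) × SD(d)/√25. Its variance is Var(Y14) + Var(Y28) - 2 Cov(Y14, Y28), all over n. Equality of the two variances is not used.

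**The plan's own figure.** N=25 comes with no effect size, SD or power, so there is nothing to reproduce. It serves only as the simulation size.

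**Simulation inputs.** From the documents: n=25, four visits, non-detects set to the LOD, on-product level about 7 log10 CFU/g. Assumed, because the documents do not give them: log10 LOD of 2 or 3; on-product mean/SD of 7/0.5, 7/1.0 or 6/1.5; Day 21-28 correlation 0.5; baseline detection 0%, 4% or 20%; Day 42 detection 20%; detectable values spread evenly over 2 log10 above the LOD at baseline and 3 log10 at Day 42. There were 4,000 trials per scenario, without dropout. Equal variance was judged by a median-centred Levene test and pooled residual normality by Shapiro-Wilk, both at 0.05.

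**Results at log10 LOD 2, all trials:**

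| Mean/SD | Baseline detection | All 25 at LOD | Equal variance fails, log | Equal variance fails, rank | 95% CI coverage, log10 |
|---|---|---|---|---|---|
| 7/0.5 | 4% | 36.2% | 85.4% | 100% | 95.0% |
| 7/0.5 | 20% | 0.4% | 28.0% | 93.6% | 94.6% |
| 7/1.0 | 4% | 36.1% | 100% | 100% | 94.9% |
| 7/1.0 | 20% | 0.4% | 95.1% | 93.7% | 94.8% |
| 6/1.5 | 4% | 36.0% | 100% | 100% | 94.9% |
| 6/1.5 | 20% | 0.3% | 100% | 88.1% | 95.0% |

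Over all 18 scenarios, coverage was 94.4-95.6%, pooled normality failed in 99.9-100% of trials, and equal variance on ranks failed in 81-100%. Ranking therefore does not cure the unequal variance.

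**Only trials with at least one detectable baseline.** Every all-LOD trial failed the log-scale variance check, so the conditional rate is (overall - all-LOD)/(1 - all-LOD). For 7/0.5 this gives (0.854 - 0.362)/(1 - 0.362) = 0.77 at 4% detection and (0.280 - 0.004)/(1 - 0.004) = 0.28 at 20%. In the other four rows it is 95-100%. A second simulation restricted to this case, under its own assumed inputs, gave failure in 48-100% on the log scale and 86-100% on ranks, with coverage of 94-96%. A wider grid over all trials went as low as 6.5% on the log scale, depending on how far the few detectable LOD-period values spread.

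**All baselines at the LOD.** Here Var(Y14) = 0 and the four-visit covariance matrix has determinant 0. In one simulated dataset, moving the baseline variance from 0.1 to 0.01, 10^-4 and 10^-8 raised the log-likelihood from 26.8 to 55.5, 113.1 and 228.2, so it has no maximum. The fallback loses nothing for Day 28 if it is on the log scale: with Y14 = LOD for everyone, mean(d) = mean(Y28) - LOD and SD(d) = SD(Y28). Estimate and interval matched in every such trial (for example 4,000 of 4,000).

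**How often the fallback is closed.** The chance that all 25 baselines are non-detectable is 0.96^25 = 0.36 at 4% detection and 0.80^25 = 0.004 at 20%. The fallback is thus unavailable in about 64% and 99.6% of trials respectively.

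**The case against.** Four points count on the other side.

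- A reader might infer that the foreseen all-LOD baseline costs the study its estimate. It does not. That failure is real, because the matrix is singular, and the SAP provides a fallback that keeps a mean and interval. What stands against it is only that its scale is unstated.
- A reader might infer that failure of the check leads automatically to ranks. The SAP says only that transformations will be considered, names no test, and plans boxplots and individual line graphs that could inform judgement. Failure is not certain either, as the low end of the simulated range shows. But a choice left open until the data are seen, in an open-label study, is a reason to fix the rule.
- A reader might infer that striking out the variance criterion is enough. It is not. In a grid of 32 scenarios, unequal variance was the sole failing check in at most 0.1% of trials; pooled normality would trigger the same sequence.
- Constant variance might mean something else, such as homogeneity across participants or a check of scaled residuals. That is possible, but the SAP does not say so.

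In addition, because the SAP starts on raw counts, the trigger is at present a route to the log scale. Removing it without making log10 primary would do harm.

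**Conclusion.** The concern holds in a bounded form. The mismatch between an unstructured covariance and an equal-variance criterion across visits is in the text and depends on no assumption. Its practical consequence arises when some but not all baselines are detectable: the log-scale checks often fail, the fallback is closed, and the only further step named gives no estimate. What can be lost is a log10 change whose paired interval covers at about 94-96%.

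The failure rates rest on assumed LOD, SD, detection rates and spread of detectable values, on complete data, and on one choice of test. Coverage refers to the mean change with non-detects counted at the LOD. The documents do not show that the estimate will be lost, only that the written sequence permits it.

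**What to change.** In SAP 8.2, before database lock:

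1. Make log10 CFU/g the primary scale for the four-visit model and for the Day 21/28 fallback, in line with the protocol synopsis.
2. Delete equal variance across visits as a trigger.
3. Replace the pooled-residual normality check with a look at the within-person log10 changes for each planned contrast: Day 14 to 21, 14 to 28, 14 to 42, and 28 to 42. The last is a secondary endpoint in SAP 5.2 but is not among the model contrasts listed in 8.2.
4. If those changes are skewed, keep the log10 estimate, add a bootstrap 95% CI, and treat any rank test as supportive only.
5. Align the trigger wording in the protocol synopsis and protocol 12.3.2. Both replace non-detects by zero, which has no logarithm, so the SAP's LOD rule has to be carried over.

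In simulated trials with at least one detectable baseline, a normality check on the Day 14 to 28 changes failed in only 4-7% at SD 1.0-1.5 and 15-27% at SD 0.5, so step 4 would be used sometimes but not routinely. Day 14 to 42 changes may be mostly zero; there the proportion returning to baseline, already planned, will say more than a mean.

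The cost is wording, a little extra analysis, and giving up the raw-scale change as the starting analysis.

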5.2. Secondary endpoint(s)

- Change in LcS number (CFU/g feces) from baseline (Visit 2; Day 14) to during the ingestion period (Visit 3; Day 21).
- Change in LcS from the end of the ingestion period (Visit 4; Day 28) and to the end of follow-up (Visit 5; Day 42)

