6.2. Per protocol (PP) population

The per protocol (PP) population is a subset of the ITT population in which subjects will be excluded for, but not limited to, the following reasons:

- Missing consumption of product for two or more days during study product ingestion period
- Not consuming the study product the day before stool collection
- Missing appointments
- Use of prohibited drugs or any products thought to alter the primary outcome variable during the study
- Not adhering to instructions as outlined in the protocol

All decisions regarding the exclusions from the PP population will be documented following the data review meeting which will occur prior to database lock.

7. Determination of sample size

Sample size was determined based on previous studies, which indicate enrolling a sample size of N=25 will provide sufficient data for a significant effect. No subjects will be replaced in the event of early terminations.

8. Statistical methods

Unadjusted descriptive statistics will be provided per measured time point. Continuous variables will be summarized with mean, standard deviation, median, and range. Categorical variables will be summarized with counts and percentages. All tests of significance are two-sided and considered significant at the 0.05 level. SAS (version 9.4 or higher) or R (version 4.2.0 or higher) will be used for statistical analyses. All analyses will be conducted for the ITT and PP populations.

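### If ranks are used and at least one baseline sample has detectable LcS, SAP 8.2 leaves the primary Day 14 to Day 28 change with a test but no planned estimate or 95% CI

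*SAP*

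**What the plan says.** SAP 8.2 sets out a sequence.

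- Non-detects: "For samples where LcS is not detected, counts will be set to the limit of detection".
- Main analysis: "LcS number over time will be analyzed with a repeated measures model with an unstructured covariance structure".
- Output: "The model derived absolute change in LcS from baseline (day 14) to each of days 21, day 28, and 42 will be estimated", with a 95% CI.
- If constant variance or normality of residuals is judged to fail, "a log transformation followed by a rank transformation will be considered".
- Under ranks: "if a rank transformation is used, contrast statements will be used to test the change from baseline but an estimate will not be calculated".
- A separate model of Days 21 and 28 gives means with 95% CIs, to be read as the increase from baseline. Its entry condition is joint: "If there are no detectable LcS levels at baseline and the repeated measure model assumptions are violated after exploring possible data transformations".

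SAP section 8 also plans descriptive statistics at each visit: "Continuous variables will be summarized with mean, standard deviation, median, and range". SAP 8.2 adds boxplots, subject line graphs and the proportions returning to baseline by Day 42 with 95% CIs.

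Protocol 12.3.2 and the Protocol synopsis promise the change with a 95% CI. Both allow a rank-based transformation, and neither says that the estimate is then dropped. SAP section 11, on changes from the Protocol, reads N/A.

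**The concern.** The study asks how well LcS survives the gut, and Protocol 4.3 frames this as a comparison with earlier studies in other countries. Protocol 4.4 gives results of such studies as counts per gram of feces. The answer therefore needs a size with its uncertainty, not only a p-value. The no-estimate rule exists only in the SAP, and it can leave the primary endpoint without the interval that both documents promise. The rescue model does not cover every case in which ranks may be used.

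**Working it through.** **1. Tracing the branches of SAP 8.2 once ranks are used**

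| Baseline LcS | Day 21/28 model | Result for Day 14 to Day 28 |
|---|---|---|
| At least one participant detectable | Closed: its first condition fails | Rank test, no planned estimate or CI |
| None detectable | Open if assumptions still fail | Day 28 mean with 95% CI, read as the increase |

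In the second row all Day 14 values equal the LOD, so they tie and share one rank. A check on simulated data of this kind gave a Day 14 rank variance of 0 and a 4x4 covariance of rank 3. The unstructured model is singular on ranks as well as on logs, so the existing Day 21/28 model should apply. The gap is the first row.

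**2. How easily the rescue closes**

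The documents give no baseline detection rate, so the per-participant probability p is assumed. N=25 is from Protocol 12.2 and SAP section 7. The chance of at least one detectable baseline is 1 − (1 − p)^25:

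- p = 1%: 22%
- p = 2%: 40%
- p = 5%: 72%
- p = 10%: 93%
- p = 20%: 99.6%

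These are chances that the rescue is unavailable, not chances that ranks are used.

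**3. Why a rank contrast cannot stand in for the estimate**

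Take 25 baseline and 25 Day 28 values, ranked together, with every Day 28 value above every baseline value. Baseline ranks average (1 + 25)/2 = 13 and Day 28 ranks average (26 + 50)/2 = 38. The difference is 25. Simulated Day 28 means of 10^4, 10^6 and 10^8 all gave 25.0. The contrast carries the ordering but not the amount recovered.

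**4. The variance trigger**

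The only effect that SAP 8.2 names in the model is time, so fitted values differ only by visit. Non-constant variance then means different variances at different visits, which an unstructured covariance already allows. Counting it as a violation pushes the analysis towards ranks without need.

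**5. What an interval would look like**

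The candidate is the paired mean log10 change d with interval d ± t(0.975, 24) × SD(d)/√25. All inputs were assumed: n=25; Day 28 log10 mean 7 (Protocol 4.4 cites about 10^7 per gram in earlier studies) with SD 0.5 or 1.0; LOD 10^2 or 10^3; 0% or 8% detectable baselines; within-subject correlation 0.3; 4,000 runs per setting.

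| Day 28 non-detects | SD | Coverage | Half-width (log10) |
|---|---|---|---|
| None | 0.5 or 1.0 | about 94-95% | 0.20-0.46 |
| 5-20% | 1.0 | about 93-95% | within 0.40-0.92 |
| 5-20% | 0.5 | 81-94% | within 0.40-0.92 |

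The range 0.40-0.92 is for both SDs together. A repeat with a different assumed distribution for detectable baselines gave closely similar figures (half-widths 0.20-0.42 and 0.39-0.91, lowest coverage about 80%). The weakest setting is SD 0.5 with about 5% non-detects, where coverage is about 81-88%. There 0.95^25 = 27.7% of trials contain no Day 28 non-detect, so their SD misses the lower tail.

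**The case against.** The strongest reply is that the path is narrow. Ranks come third, after the raw and log scales, and are only to be considered. A reader might infer that the primary result is likely to lack an estimate. The documents do not support that: they give no LOD, SD, baseline detection rate or criterion for a violated assumption, so the likelihood cannot be worked out.

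A reader might also infer that the estimate is lost when every baseline is non-detectable and the rank model is accepted. That case is close to empty, because the tied Day 14 ranks make the unstructured model singular. The SAP foresees failure in that situation and supplies the Day 21/28 model.

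A third tempting reading is that no information on size would remain. That is too strong. Per-visit means, SDs, medians and ranges, the plots and the return-to-baseline proportions are still planned. With complete data, the Day 28 mean minus the Day 14 mean is the mean change in CFU/g. The descriptive list includes no interval for that change, and the return-to-baseline proportions do not estimate it.

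What stands against the reply is that the SAP states the omission as a rule and does not leave it to judgement. When the rule applies with a detectable baseline, nothing else in the SAP restores the interval.

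**Conclusion.** The concern holds in a limited form and is worth fixing before analysis. If ranks are used and at least one participant has detectable baseline LcS, the planned 95% CI for the primary change is lost, contrary to Protocol 12.3.2 and to SAP 8.2's own main plan. This conclusion comes from the text and needs no assumed figure. The detection probabilities and interval properties above rest on assumed inputs. They show only that the rescue can close easily and that a usable interval is available, with the coverage caveat. The point affects the reporting of the primary endpoint; it does not undermine the trial.

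**What to change.** In SAP 8.2, replace the no-estimate sentence with: *If a rank transformation is used, the rank contrast will be reported together with the paired mean log10 change (non-detects at the LOD) and its t-based 95% CI, and the number of detectable samples at each visit, for Day 14 to Day 28 and for the other planned changes.*

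Three small changes go with it:

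- State that unequal variance across visits is not a violation.
- Keep the Day 21/28 model for the case where all baselines are non-detectable.
- Record the changed rank step in SAP section 11.

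The cost is a few lines and no new data. There are three downsides:

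- The estimate depends on the LOD. A ten-fold change in it moves the mean log10 change by the share non-detectable at Day 14 minus the share at Day 28. With 92% and 0% assumed, that is 0.92 − 0 = 0.92.
- A participant missing either visit does not contribute to the paired change, unlike in the likelihood-based model of SAP section 9.
- The t interval under-covers when SD is small and a few Day 28 samples are non-detectable, as shown in the working.

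Three related matters should be raised separately: the Protocol and SAP differ on whether log10 is the primary scale; they differ on zero versus the LOD for non-detects; and the secondary endpoint "Change in LcS from the end of the ingestion period (Visit 4; Day 28) and to the end of follow-up (Visit 5; Day 42") has no matching contrast among the changes listed in SAP 8.2.

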The primary outcome variable will be the change in live LcS numbers (CFU/g feces) from baseline (Visit 2; Day 14) to the end of the ingestion period (Visit 4; Day 28).

Secondary Outcome Variables

- Change in LcS number from baseline (Visit 2; Day 14) to during the ingestion period (Visit 3; Day 21).
- Change in LcS from the end of the ingestion period (Visit 4; Day 28) and to the end of follow-up (Visit 5; Day 42)

Safety Outcomes

Safety will be assessed by:

- Overall incidence of product-emergent AEs
- Number, types and duration of Serious Adverse Events (SAEs)

STATISTICAL ANALYSIS	The safety analysis will be conducted based on the modified Intention-to-Treat (ITT) population defined as all participants who receive at least one serving of the study product. The efficacy analysis will be conducted on the Per Protocol (PP) population, defined as all participants who completed the intervention in compliance.	
	The LcS number (CFU/g feces) will be evaluated with a repeated measures model. The LcS number measured at each time point will be log-transformed and included in the response vector. The absolute change from baseline to each measured time point will be estimated along with the corresponding 95% confidence interval (CI). Non-detectable levels will be replaced by zero. In the event model assumptions are violated (i.e., constant variance and/or normality of residuals), a rank-based transformation will be considered.	
STUDY PERIOD	Baseline/ run-in period (between Visit 1 and Visit 2): 14 days Study product consumption period (Visit 2-Visit 4): 14 days Follow-up period (between Visit 4 and Visit 5): 14 days	

4. Background/Rationale

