12.3 Statistical Analysis

Statistical analysis details for this study will be provided in a Statistical Analysis Plan. Briefly, all statistical analyses will be conducted using SAS for Windows (version 9.4, or higher, Cary, NC) and/or R (R Core Team 2022). Analysis populations will include intent-to-treat (ITT; all subjects randomized in the study who have consumed at least one serving of the study product) and per protocol (PP; all subjects completing the study in compliance). Safety outcomes will be evaluated on the ITT population. The PP population will serve as the primary analysis population for efficacy outcomes.

Subjects may be excluded from the PP population for non-compliance, which includes but not limited to:

- Missing consumption of product for two or more days during study product ingestion period
- Not consuming the study product the day before stool collection
- Missing appointments
- Use of prohibited drugs or any products thought to alter the primary outcome variable during the study

Not adhering to instructions as outlined in the protocol

All decisions regarding subject population and data inclusion will be documented prior to database lock.

12.3.1 12.3.1 Baseline Characteristics

Descriptive statistics [number of subjects, mean, standard deviation (SD), standard error to the mean (SEM), median, interquartile limits, minimum and maximum or frequency counts] will be presented for subject demographics and anthropometric measurements at screening/baseline for all analysis populations.

12.3.2 12.3.2 Outcome Analysis

Bacterial count will be conducted at Institute for Food Safety and Health (IFSH; Bedford Park, IL) using the culture method (FOM-LLV) and PCR approaches, and reported as CFU/g feces. The LcS number will be evaluated with a repeated measures model. The LcS number measured at each time point will be included in the response vector. The absolute change from baseline to each measured time point will be estimated along with the corresponding 95% confidence interval. Non-detectable levels will be replaced by zero. In the event model assumptions are violated (i.e. constant variance and/or normality of residuals), a rank-based transformation or log transformation (if non-zero counts) will be considered.

12.3.3 12.3.3 Safety Analysis

All AEs will be collected; however, safety will be assessed by SAEs and productemergent AEs only as reported by the subjects, as well as an assessment of vital signs.

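### The SAP's fallback model reports the Day 21/28 mean as the increase from baseline without subtracting the detection limit to which every baseline was set

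*SAP*

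**What the plan says.** SAP 8.2 handles non-detects by a single rule: "counts will be set to the limit of detection to allow for statistical analysis". The main analysis is a repeated measures model containing all time points, with changes from Day 14 estimated as contrasts. If its assumptions fail, "a log transformation followed by a rank transformation will be considered", and for ranks the SAP adds that "if a rank transformation is used, contrast statements will be used to test the change from baseline but an estimate will not be calculated".

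The SAP then anticipates a particular difficulty: "It is possible that the baseline LcS number for all subjects will be non-detectable which would likely result in the model assumption failure". If no baseline is detectable and transformation has not helped, it drops baseline and models Days 21 and 28 alone. Its only instruction for reading the output is "The estimated mean and 95% CI at day 21 and day 28 would then reflect an estimated increase from baseline". It names no scale, gives no LOD and mentions no subtraction.

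The protocol uses a different rule. Both the synopsis and section 12.3.2 state "Non-detectable levels will be replaced by zero". The synopsis also says "The LcS number measured at each time point will be log-transformed and included in the response vector", whereas section 12.3.2 starts from untransformed counts and says "a rank-based transformation or log transformation (if non-zero counts) will be considered". SAP section 11 records changes from protocol as not applicable.

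**The concern.** The two SAP rules conflict. In the fallback every baseline has been coded at the LOD, a positive number, yet the on-product mean is reported as though baseline were zero. That reading suits the protocol's zero rule on raw counts; it does not suit the SAP's LOD rule.

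The branch is realistic. A baseline made up entirely of LOD values has zero variance on the raw, log and rank scales, so none of the listed transformations can restore constant variance. Once the first condition is met, the second is likely, as the SAP itself says. The fallback's Day 28 result would then stand as the primary endpoint.

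On the log scale the headline increase could be wrong by orders of magnitude, and its interval would lie above 0 even if almost nobody shed LcS.

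**Working it through.** **Inputs.** N = 25, two-sided 0.05 (SAP 7 and 8). Expected on-product count about 10^7 per gram (Protocol 4.4, from earlier studies). The documents give no LOD, so I assume 10 to 10^4 CFU/g. Neither document gives a figure for this estimate, so there is none to reproduce.

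**Algebra.** Let L be the LOD. With every baseline coded L:
- raw change = mean(Day t) − L; the fallback reports mean(Day t), an excess of L;
- log change = mean(log10 Day t) − log10 L; the fallback reports mean(log10 Day t), an excess of log10 L.

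The main model's contrast does subtract the coded baseline. With complete data, the two routes in SAP 8.2 therefore give different answers for the same quantity.

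**Intervals.** As an approximation to the model interval with complete data, I use a one-sample t interval (t24 = 2.064). If k of 25 participants sit at one detectable level and the rest at the LOD, a distance D apart on the analysis scale, then

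SD = D × √[k(25 − k)/(25 × 24)], and half-width = 2.064 × SD/5.

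For k = 2 or k = 23, √(46/600) = 0.2769.

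- *Log, L = 100, 2 of 25 at 10^7.* Mean (2×7 + 23×2)/25 = 2.40. D = 5, SD 1.384, half-width 0.57.
- *Log, L = 10^3, 23 of 25 at 10^7.* Mean (23×7 + 2×3)/25 = 6.68. D = 4, SD 1.108, half-width 0.46.
- *Raw, L = 10^3, 2 of 25 at 10^7.* Mean (2×10^7 + 23×10^3)/25 = 800,920. Half-width about 1.14×10^6.
- *Raw, L = 10^3, 2 of 25 at 10^4.* Mean (20,000 + 23,000)/25 = 1,720. D = 9,000, SD 2,492, half-width 1,029.

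| Case | As written | After subtracting |
|---|---|---|
| Log, L = 100, 2 of 25 at 10^7 | 2.40 (1.83 to 2.97) | 0.40 (−0.17 to 0.97) |
| Log, L = 10^3, 23 of 25 at 10^7 | 6.68 (6.22 to 7.14) | 3.68 (3.22 to 4.14) |
| Raw, L = 10^3, 2 of 25 at 10^7 | 8.01×10^5 (−3.42×10^5 to 1.94×10^6) | lower by 1,000; still includes 0 |
| Raw, L = 10^3, 2 of 25 at 10^4 | 1,720 (691 to 2,749) | 720 (−309 to 1,749) |

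**Can the log interval as written ever include 0?** With detectable samples at 10^7, the lower limit is smallest at k = 1, where SD/5 = D/25 and

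lower limit = log10 L + D/25 − 2.064 × D/25 = log10 L − 1.064 × (7 − log10 L)/25.

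This gives 0.745, 1.787, 2.830 and 3.872 for L = 10, 10^2, 10^3 and 10^4. The interval therefore excludes 0 whatever the number of shedders from 0 to 25. With L = 1, log10 L = 0 and there is no error.

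**No-effect case.** If all 25 are non-detectable at Day 28, the coded change is 0, but the fallback reports an increase of L or log10 L.

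**Raw scale at expected shedding.** The excess is at most 10^4/10^7 = 0.1% of the mean.

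**The case against.** The strongest reply is that the serious error depends on a scale the SAP never assigns to the fallback. The endpoint is in CFU/g, the SAP models raw counts first, and near 10^7 the raw excess is trivial. Even a log mean, if back-transformed, would hardly be affected: 6.68 becomes about 4.8×10^6 CFU/g, of which an LOD of 10^3 is 0.02%. The fallback also states no comparison with 0. The reversals need unlikely data: with one detectable level, the subtracted log interval already excludes 0 once 4 of 25 are detectable. The path is conditional, and the analyst could stop at the rank contrast. Plots, descriptive summaries and the planned subset with LcS raised over baseline would expose a result such as 2 of 25. Finally, a non-detect truly lies between 0 and the LOD, so subtracting the LOD can understate the real raw change.

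Much of this stands. The path is conditional, the LOD is assumed, the raw error is usually negligible, and non-detects would be visible elsewhere. The excess is exact only against the coded baseline, not against the unknown true one.

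It does not remove the defect. The log scale is a live reading: the synopsis specifies it, the SAP tries it next after raw, and under ranks the SAP calculates no estimate. Back-transformation is not prescribed, and it gives a level (or, after subtraction, a ratio to the LOD) rather than the promised change. An interval presented as an increase will naturally be compared with 0 under the SAP's general significance rule. The sentence is the only instruction for this estimate, and a programmer following it would report the unsubtracted mean.

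**Conclusion.** The concern holds. Under the SAP's own coding, the fallback overstates the change by the LOD (raw) or log10(LOD) (log), and it disagrees with the main contrast in the same section. For an assumed LOD of 10 to 10^4 CFU/g, the log-scale excess is 1 to 4 log10. If shedding matches the earlier studies, the qualitative conclusion survives but the log-scale size does not; if very few participants shed, the conclusion can reverse. On raw counts near 10^7 the effect is negligible, although with low shedding it can still change the conclusion. The main repeated measures contrast is unaffected. The harm is confined to the headline estimate and interval, and arises only if the fallback is reached. The correction should be made before analysis.

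**What to change.** In SAP 8.2:
- State the fallback's analysis scale and the numerical LOD.
- Define the reported quantity as the Day 21 or Day 28 mean minus the LOD (raw), or the mean log10 count minus log10(LOD) (log). Shift both confidence limits by the same constant and compare with 0.
- Label it as change from baseline under LOD substitution. It is not a strict minimum, because a participant non-detectable at both visits has an unknown true change.
- Report the Day 21 and Day 28 means separately as levels, with the number of non-detects at each visit.

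Reconcile the protocol's zero rule (synopsis and 12.3.2) with the SAP's LOD rule, and record the difference in SAP section 11.

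The cost is two sentences in 8.2, one subtraction in the program and one entry in section 11. No new data are needed. The interval width does not change; on the log scale the stated increase becomes smaller for any LOD above 1 CFU/g.
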